6.3. Vital Signs and Physical Examination Findings

Vital signs variables including heart rate and blood pressure (systolic and diastolic) will be measured at visits as per the schedule of activities in the protocol. Descriptive statistics of the observed value and change from baseline of the vital signs will be summarized by treatment group.

Physical exam findings will not be analyzed. When physical exam findings are captured as AEs, those will be included in the analyses of AEs.

6.4. Other Safety Parameters

Weight and Waist Circumference

Descriptive statistics of changes from baseline will be summarized at selected scheduled time points.

6.5. Columbia-Suicide Severity Rating Scale (C-SSRS)

The Columbia-Suicide Severity Rating Scale (C-SSRS) will be used as a screening tool to prospectively evaluate the potential of guselkumab to induce suicidal ideation and behavior. The C-SSRS defines five subtypes of suicidal ideation and behavior in addition to self-injurious behavior with no suicidal intent and is a fully-structured subject self-report questionnaire, including standardized questions, follow-up prompts, error handling routines, and scoring conventions. The Screening version of the C-SSRS will be conducted at Screening followed by the Since Last Visit version of the C-SSRS at all other visits through the end of study.

The C-SSRS will be performed during each evaluation visit according to the assessment schedule. The C-SSRS will be performed at screening after signing informed consent, and before study agent administration, and as the first assessment for all post-baseline visits. The baseline is defined as the most severe/maximum C-SSRS score at either screening or Week 0.

In addition, potential suicide related adverse events including suicidal ideation, suicidal behavior excluding completed suicide, and completed suicide will be identified by the investigators and collected in the eCRF.

The following are C-SSRS categories and have binary responses (yes/no). A “yes” response to any C-SSRS category will be assigned a score as below:

Suicidal Ideation (1-5)

1 = Wish to be Dead

2 = Non-specific Active Suicidal Thoughts

3 = Active Suicidal Ideation with Any Methods (Not Plan) without Intent to Act

4 = Active Suicidal Ideation with Some Intent to Act, without Specific Plan

5 = Active Suicidal Ideation with Specific Plan and Intent

Suicidal Behavior (6-10)

6 = Preparatory Acts or Behavior

7 = Aborted Attempt

8 = Interrupted Attempt

9 = Actual Attempt (non-fatal)

10 = Completed Suicide

If no events qualify for a score of 1 to 10, a score of 0 will be assigned (0 = “Negative result [no suicidal ideation or behavior]”). Higher scores indicate greater severity.

The summary for suicidal ideation and behavior will be based on the safety analysis set. Suicidal ideation and behavior will be summarized based on the most severe/maximum post baseline C-SSRS outcome or AE of suicidal ideation, suicidal behavior excluding completed suicide, or completed suicide through Week 48.

The maximum score assigned for each subject will also be summarized into one of three broad categories: No suicidal ideation or behavior, suicidal ideation, suicidal behavior. A shift table for change in C-SSRS categories of no suicidal ideation or behavior, suicidal ideation, and suicidal

behavior from baseline through Week 48 will be presented, where the baseline category is based on C-SSRS score and the post baseline is based on C-SSRS and/or AE data.

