- A participant undergoing evaluation has a chest radiograph with evidence of current active TB and/or a positive QuantiFERON®-TB test result and/or 2 indeterminate QuantiFERON®-TB test results on repeat testing (refer to Section 8.2.11, Tuberculosis Evaluations) (and/or a positive tuberculin skin test result in countries in which the QuantiFERON®-TB test is not approved/registered or the tuberculin skin test is mandated by local health authorities).
- A participant receiving treatment for latent TB discontinues this treatment prematurely or is noncompliant with the therapy.
- The participant is unable to adhere to the study visit schedule or comply with protocol requirements.
- The participant has a reaction resulting in myalgia and/or arthralgia with fever and/or rash (suggestive of serum sickness and not representative of signs and symptoms of other recognized clinical syndromes) occurring 1 to 14 days after an injection of study intervention. These may be accompanied by other events including pruritus, facial, hand, or lip edema, dysphagia, urticaria, sore throat, and/or headache.
- The participant has his/her treatment assignment unblinded by the investigator.
- Sponsor decision.

Discontinuation of a participant's study intervention should be considered for:

• Participants with any type of suicidal ideation or behavior, or any self-injurious behavior, who are deemed to be at risk by the investigator. Discussion of such participants with the medical monitor or designee is required. For participants who report Suicidal Ideation with Intention to Act ("Ideation level 4"), suicidal ideation with specific plan and intent ("Ideation level 5"), suicidal behavior (actual suicide attempt, interrupted suicide attempt, aborted suicide attempt, or preparatory behaviors for making a suicide attempt) or any self-injurious behavior on a post-baseline C-SSRS assessment, the investigator risk assessment must be based upon evaluation by a mental health professional (see Section 8.2.5).

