8.2.5. Columbia-Suicide Severity Rating Scale (C-SSRS)

The C-SSRS defines 5 subtypes of suicidal ideation and 4 possible suicidal behaviors, as well as non-suicidal self-injurious behavior and completed suicide. It will be used as a screening tool to prospectively evaluate suicidal ideation and behavior in this study, as part of a comprehensive evaluation of safety. The C-SSRS is an investigator-administered questionnaire. ^{13,15}Two versions of it will be used in this study: the 'Baseline/Screening' version of the C-SSRS (see Appendix 15, [Section 10.15])will be conducted during the screening visit and the 'Since Last Visit' version of the C-SSRS (see Appendix 16, [Section 10.16]) will be completed at all other visits through the end of the study.

The investigator or trained study-site personnel will interview the participant and complete the C-SSRS. The C-SSRS will be provided in the local languages in accordance with local guidelines.

At screening and after obtaining informed consent, the C-SSRS will be the first assessment performed, before any other study procedure. At all subsequent visits, the C-SSRS will be performed according to the Schedule of Activities (Section 1.3) and should be performed before any tests, procedures, or other consultations, with the exception of the urine pregnancy test, to prevent influencing participant perceptions. Participants will be interviewed by the investigator or trained study-site personnel in a private, quiet place.

At the conclusion of each assessment, the trained personnel administering the C-SSRS will determine the level of suicidal ideation or behavior, if any. They will then determine the next course of action if any level of suicidal ideation or behavior is reported. The participant should not be released from the site until the C-SSRS has been reviewed by the investigator and the participant's risk has been assessed and follow-up determined, as appropriate.

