revenge or a reaction from others? Or both? (1) Completely to get attention, revenge or a reaction from others (2) Mostly to get attention, revenge or a reaction from others (3) Equally to get attention, revenge or a reaction from others and to end/stop the pain	(4) Mostly to end or stop the pain (you couldn't go on living with the pain or how you were feeling) (5) Completely to end or stop the pain (you couldn't go on living with the pain or how you were feeling) (0) Does not apply	45	

© 2008 Research Foundation for Mental Hygiene, Inc.

C-SSRS—Since Last Visit (Version 1/14/09)

Page 1 of 2

SUICIDAL BEHAVIOR	Since
(Check all that apply, so long as these are separate events; must ask about all types)	Last Visit
Actual Attempt: A potentially self-injurious act committed with at least some wish to die, as a result of act. Behavior was in part thought of as method to kill oneself. Intent does not have to be 100%. If there is any intent/desire to die associated with the act, then it can be considered an actual suicide attempt. There does not have to be any injury or harm, just the potential for injury or harm. If person pulls trigger while gun is in mouth but gun is broken so no injury results, this is considered an attempt. Inferring Intent: Even if an individual denies intent/wish to die, it may be inferred clinically from the behavior or circumstances. For example, a highly lethal act that is clearly not an accident so no other intent but suicide can be inferred (e.g., gunshot to head, jumping from window of a high floor/story). Also, if someone denies intent to die, but they thought that what they did could be lethal, intent may be inferred.	Yes No
Have you made a suicide attempt?	
Have you done anything to harm yourself? Have you done anything dangerous where you could have died? What did you do? Did you as a way to end your life? Did you want to die (even a little) when you? Were you trying to end your life when you ?	Total # of Attempts
Or Did you think it was possible you could have died from?	
Or did you do it purely for other reasons / without ANY intention of killing yourself (like to relieve stress, feel better, get sympathy, or get something else to happen)? (Self-Injurious Behavior without suicidal intent) If yes, describe:	
Has subject engaged in Non-Suicidal Self-Injurious Behavior?	Yes No □ □
Interrupted Attempt:	

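### SAP 6.5 leaves the C-SSRS item on non-suicidal self-injury out of every planned suicidality summary

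*SAP*

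**What the plan says.** SAP 6.5 introduces the instrument this way: "The C-SSRS defines five subtypes of suicidal ideation and behavior in addition to self-injurious behavior with no suicidal intent". It then codes a yes answer as 1 to 5 for the ideation levels and 6 to 10 for preparatory acts up to completed suicide. For everyone else, "If no events qualify for a score of 1 to 10, a score of 0 will be assigned". That score is labelled a negative result, with a bracketed gloss that neither suicidal ideation nor suicidal behavior was found. The maximum score is then "summarized into one of three broad categories: No suicidal ideation or behavior, suicidal ideation, suicidal behavior", and the shift table uses the same three categories from baseline through Week 48. Adverse events can also count on the post-baseline side, but only three types: suicidal ideation, suicidal behavior short of completed suicide, and completed suicide.

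Protocol 8.2.5 says that the C-SSRS covers ideation and suicidal behavior "as well as non-suicidal self-injurious behavior and completed suicide". The Since Last Visit form in protocol Appendix 16 has a separate yes/no item for it: "Has subject engaged in Non-Suicidal Self-Injurious Behavior". The Schedule of Activities (protocol 1.3) places the C-SSRS at screening and at every visit from Week 0 to Week 48. Protocol 7.1 describes those in whom discontinuation is to be weighed: "Participants with any type of suicidal ideation or behavior, or any self-injurious behavior, who are deemed to be at risk by the investigator".

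**The concern.** The protocol collects this item prospectively and acts on it, but the SAP gives it no place in the results. Take a participant with a clean baseline who reports self-injury without suicidal intent during the study and is assessed for risk. That participant would read none-to-none in the shift table, exactly like someone who reported nothing.

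Safety and tolerability are part of the primary objective, and the protocol synopsis lists suicidality assessment among the safety data to be summarized. The value of the C-SSRS is that every participant is asked the same question at every visit. If one of its items is never tabulated, the systematic answer by arm is lost from the analysis built on that instrument.

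**Working it through.** No sample-size, power or event figure is at issue, and the plan gives none to reproduce. The check applies the SAP 6.5 rule as written and compares it with the protocol.

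**Step 1: the rule.** Score = the largest code from 1 to 10 among a participant's findings, or 0 if there is none. Category: 0 = none, 1 to 5 = ideation, 6 to 10 = behavior. NSSIB has no code.

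**Step 2: four test profiles.**

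| Findings | Score | Category | NSSIB shown under SAP 6.5? | NSSIB shown if counted separately? |
|---|---|---|---|---|
| None | 0 | none | not applicable | no (correct) |
| NSSIB only | 0 | none | no | yes |
| NSSIB and ideation level 2 | max(2) = 2 | ideation | no | yes |
| NSSIB and actual attempt | max(9) = 9 | behavior | no | yes |

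The first two rows cannot be told apart in the planned output. In the last two the score is right, but the self-injury is still not reported. The gap is therefore not confined to participants with NSSIB alone.

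**Step 3: what the protocol counts as no finding.** In protocol 8.2.5 the no-action category after Week 0 covers participants without suicidal ideation or behaviors, and its parenthesis includes self-injury without suicidal intent among the behaviors that must be absent. The next category confirms this reading: it puts NSSIB with ideation levels 1 to 3, for investigator risk assessment. The SAP tabulates ideation levels 1 to 3 but not NSSIB. Its score-0 group is thus wider than the protocol's no-action group, and the difference is exactly the NSSIB-only participants.

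**Step 4: stopping.** In 8.2.5 the paragraph on interruption or discontinuation covers ideation levels 4 and 5 and suicidal behavior only. Self-injury enters through 7.1, and only for participants judged at risk. The two sections also differ on when the risk assessment must rest on a mental health professional's evaluation. They should be reconciled, but the reporting gap does not depend on how.

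**Step 5: the adverse event route.** Protocol 8.2.5 sends a C-SSRS finding to the AE page if the investigator considers it new or worsening and clinically significant. Protocol Appendix 6 defines an AE broadly and requires every AE to be recorded whatever its severity, so an act of self-injury may also be reported in its own right. SAP 6.1 analyzes all treatment-emergent AEs. However, none of the three AE types admitted to the SAP 6.5 summary is NSSIB, so an AE report does not change the score, the category or the shift.

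**Step 6: other outputs.** No other SAP section names NSSIB, and no listing is planned for it.

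**The case against.** The strongest reply is that the scoring does what it says. SAP 6.5 states its aim as suicidal ideation and behavior, and score 0 is glossed as the absence of those two. By definition NSSIB is neither, so the label is literally true. The protocol does not promise an NSSIB table, and protocol 9.4.3 leaves safety details to the SAP, so no protocol commitment is broken. A trigger for assessing an individual is not automatically a required table. Self-injury events can also reach the AE tables by arm, the listings of serious and severe AEs and of AEs leading to discontinuation, and the DMC's safety review.

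All of this stands, and it rules out several stronger readings:

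- A reader might infer that score 0 is a coding error. It is not. What is missing is a separate count.
- A reader might infer that the trial cannot show any difference between arms in self-injury. That is true of the C-SSRS outputs only, because the general AE tables may show reported events.
- A reader might infer that 8.2.5 makes NSSIB a ground for discontinuation. It calls for risk assessment. Discontinuation comes in through 7.1, for participants judged at risk.
- A reader might apply an assumed rate, say 1% to 3% of 180 participants (1.8 to 5.4). Nothing in the documents supports such a rate. For the participants grouped with those who have no finding, it would have to be the rate of NSSIB with no scored finding, and exclusion criterion 27 already keeps out those with NSSIB at screening who are judged at risk.

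The reply does not supply the C-SSRS answer itself. An AE term depends on what is reported and how it is coded, whereas the C-SSRS item is a fixed question put to everyone.

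**Conclusion.** The point holds as a gap in reporting. Followed as written, SAP 6.5 shows NSSIB in none of its suicidality outputs and groups NSSIB-only participants with those who have no finding, although the protocol separates the two groups for risk assessment.

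The number of participants affected cannot be computed from the documents. Any count is likely to allow description only, which fits SAP section 6, where no formal safety comparison is planned. The primary endpoint, the multiplicity procedure and the existing C-SSRS score are unaffected.

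The conclusion rests on two readings: that the code list in SAP 6.5 is complete, and that no NSSIB output is planned outside the protocol and SAP.

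**What to change.** Leave the 0 to 10 score and the three categories as they are. Add to SAP 6.5 a separate n (%) of participants with NSSIB = yes, at baseline and at any post-baseline visit, by actual treatment group, with a listing of those participants.

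Present it for both SAP section 6 periods, using that section's rules for assigning events to groups. The Week 16 display is needed because only that period's list of groups has a placebo column, while the SAP 6.5 summary is specified through Week 48.

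State how baseline NSSIB is defined. The screening form in protocol Appendix 15 records behavior both over the lifetime and over the past 6 months, so the recall period has to be named.

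The cost is SAP wording, one extra row and one listing. The data are already on the form, and no clinical rule, data collection or efficacy analysis changes. The text is best settled before the Week 16 database lock, after which selected sponsor personnel are unblinded.

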7. PHARMACOKINETICS/PHARMACODYNAMICS

7.1. Pharmacokinetics

All PK analyses will be based on the PK analysis set (Section 2.4.3). Unless otherwise specified, tabular summaries of PK for key study periods are in general presented as following:

Summaries through Week 16:

PK data through Week 16 will be summarized by treatment groups

- Guselkumab 200 mg SC
- Guselkumab 1200 mg IV

Summaries through Week 48:

PK data through Week 48 will be summarized by treatment groups including

- Placebo → 100 mg SC
- Placebo → 200 mg SC
- Guselkumab 200 mg SC
- Guselkumab 1200 mg IV

7.1.1. Serum Guselkumab Concentrations

Blood samples for measuring serum guselkumab concentrations will be collected from all participants at the specified visits as shown in the schedule of activities in the protocol. Serum samples will also be collected at the final visit from participants who terminate study participation early. Samples must be collected before study agent administration at visits when a study agent administration is scheduled. In addition, for IV infusion-related visits (i.e., Weeks 0, 4, and 8), another blood draw should be taken approximately 60 minutes after completion of the infusion for serum concentration of guselkumab.

Serum guselkumab concentrations will be summarized using descriptive statistics, including n, arithmetic mean, SD, coefficient of variation (%CV), median, interquartile range, range (minimum and maximum), by treatment group at each PK sampling time where appropriate. PK data may be displayed graphically. The following analyses will be performed as appropriate:

- Summary of serum guselkumab concentrations at each visit by treatment group
- Proportion of participants without detectable serum guselkumab concentration (below the lower limit of quantification) at each visit by treatment group
- Summary of serum guselkumab concentrations at each visit by treatment group and baseline body weight (quartiles). Other covariates may also be applied, e.g. Diabetes or BMI status (normal, overweight, obese).

- Summary of serum guselkumab concentrations at each visit by treatment group and baseline Hurley stage status
- Summary of serum guselkumab concentrations by baseline AN count category (3 to 5, 6 to 10, ≥ 11)
- Plot of median serum guselkumab concentrations over time by treatment group
- Plot of median serum guselkumab concentrations over time by treatment group by baseline body weight (\leq median, $>$ median)

7.1.1.1. Data Handling Rules

Unless otherwise specified, the following data handling rules will apply to PK analyses:

- Participants will be analyzed according to the treatment groups that they actually received.
- All serum concentration summaries for a particular timepoint will include data obtained from treated participants at the timepoint of interest without imputing any missing data.
- A concentration not quantifiable (below the lower limit of quantification) will be treated as 0 in the summary statistics and shown as the lower limit of quantification ($<$ LLOQ) in the data listings.
- The data from a subject who meets 1 of the following dosing deviation criteria will be excluded from the by-visit data analyses from that point onwards:
 - Discontinue guselkumab administrations.
 - Skipped a guselkumab administration.
 - Received an incomplete/ incorrect dose.
 - Received an incorrect study agent.
 - Received an additional guselkumab dose.

In addition, if a subject has an administration outside of dosing windows (Table 3), the concentration data collected at and after that visit will be excluded from the by-visit data analyses. Additional exclusions for incongruous PK data to be implemented based on Janssen SOP-07948. All participants and samples excluded from the analysis will be clearly documented in the Clinical Study Report.

Table 3: Dosing Window	
Visit	Window
Week 0 through Week 36	± 7 days from scheduled visit day
Final Safety and Efficacy Follow-up visits	± 14 days from scheduled visit day

7.1.2. PK vs Efficacy/Safety

The relationship between serum guselkumab concentrations and safety or efficacy endpoints may be explored, e.g.:

- The relationship between serum guselkumab concentrations (quartiles) and proportion of participants achieving HiSCR and change from baseline in AN count at Week 16, and Week 40 will be explored. Summaries by baseline body weight (\leq median, $>$ median) or baseline Hurley stage status may also be provided.

7.1.3. Population PK Analysis

When appropriate, population PK analysis will be performed using serum guselkumab concentration-time data in all randomized participants with the nonlinear mixed-effects modeling (NONMEM) approach. Details will be provided in a separate technical report.

7.2. Immunogenicity

Immunogenicity analyses will be based on the Immunogenicity Analysis Set (Section 2.4.4). Participants will be analyzed according to the treatment groups that they actually received. No imputation for missing concentration data will be performed.

Unless otherwise specified, tabular summaries of immunogenicity for key study periods are in general presented as following:

Summaries through Week 16:

PK data through Week 16 will be summarized by treatment groups

- Guselkumab 200 mg SC
- Guselkumab 1200 mg IV
- Combined Guselkumab

Summaries through Week 48:

PK data through Week 48 will be summarized by treatment groups including

- Placebo \rightarrow 100 mg SC
- Placebo \rightarrow 200 mg SC
- Guselkumab 200 mg SC
- Guselkumab 1200 mg IV
- Combined Guselkumab

7.2.1. Antibodies to Guselkumab

Blood samples will be collected to examine the formation of antibodies to guselkumab at the specified visits as shown in the schedule of activities in the protocol. Serum samples will also be collected at the final visit from participants who terminate study participation early.

The antibodies to guselkumab status (positive at any time, negative) and titers will be summarized by treatment group for participants who receive at least one dose of guselkumab and have appropriate samples for detection of antibodies to guselkumab. The maximum titers of antibodies to guselkumab will be provided for participants who are positive for antibodies to guselkumab.

A listing of participants who are positive for antibodies to guselkumab will be provided. This listing will provide information regarding dose administered, injection-site/infusion reactions, guselkumab serum concentration, and antibody status for all visits.

